#### **Research Design**

Patients who have 0 and 2 hour troponins ordered will have their chart reviewed by the research coordinator for candidacy in the study (see below for inclusion/exclusion). If the patient meets study entry criteria then platelet aggregation studies using arachidonic acid will be added on to the 0 and 2 hour lab draw.

The study will compare the 0 and 2-hour platelet aggregation scores of patients receiving aspirin who are undergoing two sets of troponin tests. The first group will consist of patients not receiving any narcotics, the second group will include those receiving morphine, and the third group will include those receiving fentanyl. The treating clinician will determine the appropriate pain treatment plan for each patient.

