### Sample/Participants

The research coordinator will perform chart review on Emergency Department patients presenting with chest discomfort. If there are 2 sets of troponins ordered and no exclusion criteria then the research coordinator will approach the patient for consent.

Inclusion criteria: Adult Emergency Department patients undergoing 0 and 2 hour troponin testing who have been administered aspirin within 30 minutes of the initial blood draw. Initially all patients undergoing this testing will be candidates for the study. We will attempt to enroll 80 patients in the each of the 3 arms. Determination of which (if either) narcotic is administered will be up to the clinician. As we reach the enrollment goals our research coordinator will discuss with the clinicians the expected pain plan to tailor enrollment of patients in the treatment arms that are still needed

Exclusion criteria: Patients not expected to get a 2 hour troponin; patients already on aspirin, clopidogrel, or stronger anti-coagulants; patients who arrived via EMS given it can be difficult to find the run reports to determine whether patient received fentanyl in the pre-hospital period; pregnant patients; patients on chronic narcotics; patients already once enrolled in this study, inability to provide consent in English

With regards to at risk populations, Economically Disadvantaged, Nursing home residents, prisoners, homeless patients are all commonly encountered in the ED. However, the request of 1 or 2 blue top tubes (totaling about a teaspoon of blood) is not an onerous ask. Since narcotic use (or non-use) will be wholly up to the provider and not impacted by this study we see no problems with including them.

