#### Instrumentation-Data collection

If consent is given to obtain the labs then the research coordinator will extract basic demographic information into a spreadsheet (name, MRN, age, sex, race, ethnicity), as well as the results of the labs including the CBC data already obtained (hemoglobin and platelet count). We will record the patients' creatinine to also help describe our population. Finally the platelet aggregation data that we are studying will be recorded, as well as confirmation with the patient that they are not on anti-platelet medicines such as aspirin, clopidogrel (Plavix), aspirin-dipyridamole (Aggrenox), prasugrel (Effient), ticagrelor (Brilinta). We will record time and dosing of aspirin administration, time and dosing of narcotic medicines (morphine, fentanyl, dilaudid).

This spreadsheet would be maintained on SH-Lakeland servers in a location only accessible to the research coordinator and PI.

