# **Data Analysis Procedure**

In the PACIFY trial, at 2 hours, patients receiving fentanyl had a PRU value of 113 +/- 94 on the platelet aggregation study (light aggregometry using ADP) after receiving Brilinta (ticagrelor), versus 71 +/- 66 in those not receiving fentanyl. With an alpha of 0.05 and beta of 0.8, 57 patients would be required to demonstrate statistical significance if there is a similar magnitude of effect. In the PERSEUS trial at 2 hours, patients receiving fentanyl had a PRU value of 173 +/-90 after also receiving Brilinta (ticagrelor), versus 210 +/- 76 in those receiving morphine and Brilinta (ticagrelor). 74 patients would be required to show statistical significance in direct comparison of morphine vs fentanyl. The aim is to enroll 80 patients in each arm (no narcotic, morphine, and fentanyl).

Two-tailed T-testing will be used to look for differences in the 2 hour platelet reactivity response rates between those receiving morphine versus those not receiving narcotics and between those receiving fentanyl and those not receiving narcotics.

If the data is sent to the Spectrum Health SASS team for analysis MRN's will be converted to a study ID so that the actual MRN will not be sent out.

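### Clinicians choose the comparison groups, but the only planned analysis is two t-tests at 2 hours, with no adjustment and no stated role for the 0-hour value

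*Combined protocol and SAP*

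**What the plan says.** - **How groups arise.** Research Design: "The treating clinician will determine the appropriate pain treatment plan for each patient". Sample/Participants repeats this: "Determination of which (if either) narcotic is administered will be up to the clinician". As the enrolment targets are approached, "our research coordinator will discuss with the clinicians the expected pain plan to tailor enrollment" towards the arms still short of patients. The target is 80 per arm.
- **What is compared.** Research Design: "The study will compare the 0 and 2-hour platelet aggregation scores of patients receiving aspirin". Data Analysis Procedure: "Two-tailed T-testing will be used to look for differences in the 2 hour platelet reactivity response rates", with two contrasts, morphine versus no narcotic and fentanyl versus no narcotic. That section names no covariate, baseline value, regression, matching or weighting.
- **What is recorded.** Instrumentation-Data collection lists age, sex, race, ethnicity, hemoglobin, platelet count and creatinine. It adds: "We will record time and dosing of aspirin administration, time and dosing of narcotic medicines". No use in the comparison is stated for any of these; creatinine is there to describe the population. Blood-draw times and pain severity are not listed.
- **Aspirin timing.** Patients are eligible "who have been administered aspirin within 30 minutes of the initial blood draw". Whether aspirin comes before or after that draw is not said.
- **Exclusions.** Patients already on aspirin, clopidogrel or stronger anti-coagulants, those on chronic narcotics and those arriving by EMS are excluded.

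**The concern.** Patients given an opioid for chest pain are likely to differ from those who are not, and the plan has no step to account for this. A t-test at 2 hours attributes the whole difference between groups to the narcotic. If the groups already differ in something that predicts 2-hour aggregation, and nothing offsets it, the contrast is biased and the 5% error rate no longer holds. The study hypothesis is causal (that both narcotics reduce aspirin's effectiveness), so both planned tests are exposed.

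The undefined outcome adds to this. The term *response rates* could mean the 2-hour level or the change from 0 to 2 hours. Two analysts could run different primary tests from the same text, and the choice could be made after the data are seen. The value that would help most, 0-hour aggregation, is already being measured in every patient.

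**Working it through.** **1. What the plan's own sizing assumes.** Inputs from Data Analysis Procedure (PACIFY, ticagrelor with ADP): 113, SD 94, with fentanyl; 71, SD 66, without. The difference is 42 and the average SD is (94 + 66)/2 = 80. With two-sided alpha 0.05 and 80% power, n per arm = 2 × (80 × 2.802 / 42)² = 56.95, or 57. This reproduces the stated 57. (The root-mean-square SD, 81.22, gives 59.) The sample size therefore rests on an unadjusted comparison of 2-hour means.

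**2. Illustration of bias.** Two inputs are assumptions, because neither is in the documents: g, the systematic 0-hour gap between groups in SD units, and ρ, the correlation of 0-hour with 2-hour values. I also assume equal SDs at both times, 80 per arm, no true effect, and a gap that acts only through the 0-hour value.

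- Level reading: bias b = g × ρ.
- Change reading: bias = −g × (1 − ρ). The SD of change is √(2(1 − ρ)), so the standardised size is b = g × √((1 − ρ)/2), with opposite sign.
- False-positive rate = P(|Z + b√(80/2)| > 1.96).

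Worked case, g = 0.25 and ρ = 0.5, level reading: b = 0.125 and 0.125 × 6.325 = 0.791. The rate is P(Z > 1.169) + P(Z < −2.751) = 0.121 + 0.003 = 12.4%.

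| Reading | Gap | ρ = 0.1 | 0.3 | 0.5 | 0.7 |
|---|---|---|---|---|---|
| 2-hour level | 0.25 SD | 5.3% | 7.6% | 12.4% | 19.8% |
| 2-hour level | 0.5 SD | 6.2% | 15.8% | 35.3% | 60.0% |
| Change | 0.25 SD | 18.5% | 15.5% | 12.4% | 9.4% |
| Change | 0.5 SD | 56.4% | 46.5% | 35.3% | 23.2% |

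On the level reading the rate reaches 10% when g × ρ = 0.103, that is, at a gap of 0.34, 0.21 or 0.15 SD for ρ = 0.3, 0.5 or 0.7. At ρ = 0.1 the inflation is small. Taking the change score does not remove the problem; it reverses the direction of the bias.

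**3. Chance imbalance is a different matter.** The SD of a chance gap is √(2/80) = 0.158, so a gap of 0.25 SD or more arises by chance 11.4% of the time. That is already allowed for in the test, and the overall rate stays at 5%. Only a systematic gap raises it.

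**4. What adjustment achieves.** If the 0-hour value carries the whole gap, ANCOVA returns the rate to about 5%, by construction. If it carries only half of the 2-hour gap, simulation (20,000 replicates, ρ from 0.3 to 0.7) gives 7.1% to 8.3% where the t-test gives 12.4% (total 2-hour gap 0.125 SD). It gives 13.0% to 19.7% where the t-test gives 35.3% (0.25 SD). The bias is reduced, not removed.

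**5. Aspirin timing.** With aspirin up to 30 minutes either side of the first draw, exposure at a nominal 2-hour draw is 2.0 ± 0.5, or 1.5 to 2.5 hours. The 0-hour sample may also be pre-aspirin in some patients and post-aspirin in others.

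**The case against.** - **The bias sizes are assumed.** This stands. Neither g nor ρ is in the documents, and the level-reading rates run from 5.3% to 60.0% according to the pair chosen. They show how bias would arise, not how large it is. The exclusions also remove some of the likeliest sources of imbalance, though they do not balance the groups.
- **Research Design and Data Analysis Procedure need not conflict.** A reader might infer that the two sections contradict each other on the 0-hour value. They do not have to: if *response* means the 0-to-2-hour change, they agree. The defect is an undefined endpoint.
- **Timing may be harmless.** A reader might infer that the 1.5-to-2.5-hour range, or the steering of later enrolment, itself biases the results. Aspirin timing biases a contrast only if it differs by arm, and calendar time only if aggregation or care also drifts. Nothing in the documents shows either.
- **The plan never says its tests are unadjusted.** True. This is inferred from the choice of t-test and the absence of any adjustment, but no other reading of the section is apparent.

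None of this answers the design point: clinician-chosen groups, no planned control of confounding, and a collected 0-hour value left without a role.

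**Conclusion.** The concern holds, on the design alone. The groups are non-randomised, the only planned analysis is two t-tests with no adjustment, and the endpoint can be read in two ways. A systematic difference in starting platelet reactivity, or in aspirin timing if it differs by arm, could be reported as a narcotic effect under either reading. Both planned contrasts are affected.

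The size cannot be stated from the documents. The 12.4% at an assumed 0.25 SD gap and correlation of 0.5 is an illustration. It should not be read as evidence that these groups will be imbalanced, or in which direction. Nor would adjustment make the comparison causal: pain severity is not recorded, so confounding by indication would remain.

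**What to change.** In Data Analysis Procedure:

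1. Define the endpoint as 2-hour aggregation, and state the role of the 0-hour value.
2. Make the primary analysis a linear model (ANCOVA) in all enrolled patients, on group (three levels), 0-hour aggregation and a short prespecified set of covariates already recorded, for example age, sex, platelet count and aspirin dose. Take both planned contrasts from it, with standard errors that allow unequal variances.
3. Log actual draw times. With the recorded aspirin times, include an indicator for whether the 0-hour sample came before or after aspirin, and the interval from aspirin to the 2-hour draw.
4. As a sensitivity analysis only, repeat the model in patients whose 0-hour sample preceded any narcotic. Report the number excluded per arm, and note that this rule can remove patients only from the two narcotic arms and so may itself alter comparability.
5. Keep the t-tests as supportive, and word conclusions as associations.

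**Cost.** SAP wording, one added data item and a few degrees of freedom. The primary model loses no patients by design. On the plan's PACIFY inputs, with 80 no-narcotic patients, unadjusted Welch power for fentanyl versus none is 90%, 83% or 70% with 80, 60 or 40 fentanyl patients, which shows what the restricted analysis could lose. Power of 80% needs 54 fentanyl patients unadjusted, or 48 or 38 with baseline adjustment at ρ = 0.3 or 0.5 (SDs multiplied by √(1 − ρ²)). The adjusted figures are optimistic, because they ignore the variance inflation that arises when covariates correlate with group.

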# Introduction or Background

#### Problem and Purpose Statement-Objective of the Research

The aim of this project was to determine whether fentanyl and morphine have similar effects in reducing aspirin's effect upon platelets in emergency department patients with chest discomfort. Morphine has been shown to worsen outcomes in heart attack patients due to reduction of oral anti-platelet agent effectiveness and so many providers have switched to using fentanyl. However, it is largely unknown whether fentanyl has similar effects.

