## **Research Questions or Hypothesis**

It is unlikely that a sufficient sample of patients with acute coronary syndrome (ACS) can be obtained to prospectively compare fentanyl to morphine, as the administration of other anticoagulants would confound the results. Therefore, the study will focus on chest pain patients in the emergency department. The hypothesis is that both morphine and fentanyl will reduce the effectiveness of aspirin.

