## Methodology

Given the challenges in obtaining a sufficient sample of patients with acute coronary syndrome (ACS) to prospectively compare fentanyl to morphine, the study will focus on chest pain patients in the emergency department. These patients typically have blood drawn initially and again two hours later to check for elevation and changes in troponin levels, a cardiac muscle protein detectable when cardiac muscle is being injured. These blood draws will be supplemented by evaluating platelet aggregation at the 0 and 2-hour marks.

There are many measures and techniques in evaluation of platelet function. Light Transmission Aggregometry (LTA) looks at changes in light transmittance through serum as platelets aggregate, leading to increased light transmission as more platelets aggregate. Aspirin interferes with arachidonic acid mediated aggregation because of its effects upon COX-1 conversion of arachidonic acid to thromboxane A2. Arachidonic acid is therefore the best trigger to use to evaluate aspirin's effect upon platelets, as opposed to epinephrine, ADP, or several others used to evaluate the stronger anti-platelet oral and IV agents that act in different places in the platelet activation cascade (8).

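### The plan aims at and sizes a fentanyl-versus-morphine comparison, but the listed tests compare each drug only with no narcotic

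*Combined protocol and SAP*

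**What the plan says.** Four places in the combined protocol and SAP bear on the comparison between the two drugs.

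- **Problem and Purpose Statement.** The aim is to "determine whether fentanyl and morphine have similar effects" in reducing aspirin's effect on platelets.
- **Methodology.** The population is explained by the difficulty of finding enough patients with acute coronary syndrome "to prospectively compare fentanyl to morphine, the study will focus on chest pain patients".
- **Data Analysis Procedure, sizing paragraph.** A figure of 74 patients is given for "statistical significance in direct comparison of morphine vs fentanyl", using 2-hour means and SDs from a cited ticagrelor trial of fentanyl against morphine. The target is then 80 in each of three arms.
- **Data Analysis Procedure, test paragraph.** Two-sided t-tests of the 2-hour platelet result are planned "between those receiving morphine versus those not receiving narcotics and between those receiving fentanyl and those not receiving narcotics". No third contrast is listed.

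The Research Questions or Hypothesis section states the formal hypothesis: "both morphine and fentanyl will reduce the effectiveness of aspirin". Research Design names the three groups and says that their 0- and 2-hour scores will be compared, without naming any pairwise contrast. On treatment choice it says: "The treating clinician will determine the appropriate pain treatment plan for each patient". No section gives a between-drug test, a confidence interval for the difference, or an equivalence margin.

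**The concern.** The aim, the reason for the population and the larger of the two sizing figures all point to fentanyl against morphine, and the list of tests leaves that contrast out. Followed literally, the plan ends with two results against a shared control and nothing that compares the drugs with each other.

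The purpose statement says that many clinicians have moved from morphine to fentanyl, so readers will want to know how the two compare. Without a specified analysis, they may be left to judge this from which control comparison reached significance, and that pattern can mislead in either direction. The alternative is a between-drug estimate whose status, alpha and interpretation are settled only after the results are known.

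**Working it through.** **Step 1. The plan's own sizing figures.** Inputs from the Data Analysis Procedure: alpha 0.05 and power 0.80 (the text writes beta of 0.8, read here as power). These are stated beside the first calculation and assumed to apply to the second. Two-sided testing comes from the test paragraph, and the counts are read as per arm. Formula: n per arm = 2 × [SD × (1.960 + 0.842) / difference]².

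- Fentanyl against no fentanyl: 113 − 71 = 42; pooled SD = √((94² + 66²)/2) = 81.2; n = 58.7, so 59. The simple mean of the SDs, 80, gives 56.95, so 57, the stated figure.
- Morphine against fentanyl: 210 − 173 = 37; pooled SD = √((90² + 76²)/2) = 83.3; n = 79.6, so 80 (81 with the t distribution). The stated 74 is not reproduced from these SDs. An SD of 80 gives 73.4, so 74, which suggests that the SD from the first calculation was carried over. That is an inference and a separate matter.

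The direct comparison therefore has the larger stated requirement (74 against 57), and it is the one closer to the target of 80.

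**Step 2. Comparisons named against tests specified.**

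| Comparison | Where it is called for | Test specified? |
|---|---|---|
| Morphine v no narcotic | Hypothesis | Yes |
| Fentanyl v no narcotic | Hypothesis; sized at 57 | Yes |
| Fentanyl v morphine | Purpose statement; sized at 74 | No |

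**Step 3. Can the two listed tests stand in for the third?** The control mean cancels in (fentanyl − control) − (morphine − control), so the point estimate can be recovered from the group means. Its uncertainty cannot be read from the two control p-values.

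Take 80 per arm and equal SDs, and work in SD units so that no ticagrelor data are used:

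- SE of a difference = √(2/80) = 0.158 SD.
- Critical t (158 df) = 1.975.
- Significance threshold and 95% CI half-width = 1.975 × 0.158 = 0.312 SD.

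Two hypothetical results:

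| Observed shifts from control (SD) | p against control | Between-drug difference (SD) | 95% CI | p |
|---|---|---|---|---|
| 0.30 and 0.33 | 0.060 and 0.038 | 0.03 | −0.28 to 0.34 | 0.85 |
| 0.33 and 0.80 | 0.038 and <0.001 | 0.47 | 0.16 to 0.78 | 0.003 |

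In the first row the control tests split although the drugs are almost identical. In the second they agree although the drugs differ. Only the direct contrast separates the two cases.

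**Step 4. What the direct contrast would deliver at the planned size.** This step assumes that the ticagrelor figures carry over to arachidonic-acid aggregation after aspirin. Standardised difference = 37/83.3 = 0.444.

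| Per arm | Two-sided alpha | Power (t) | Power (normal) |
|---|---|---|---|
| 80 | 0.05 | 79.7% | 80.2% |
| 74 | 0.05 | 76.6% | 77.1% |
| 80 | 0.05/3 = 0.0167 | 65.2% | 66.1% |

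**The case against.** The best defence is that the purpose statement can be read qualitatively: morphine is believed to blunt oral antiplatelet drugs, and the question is whether fentanyl does so too. The only formal hypothesis says just that, and the two listed tests match it. This reading is reasonable, and it stands to the extent that the formal hypothesis is properly covered. It does not explain why the Data Analysis Procedure computes a sample size for a direct comparison that it then does not analyse.

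A reader might infer that any between-drug result would be a contrast invented after the data were seen. The documents do not support that. The sizing paragraph names the contrast in advance, with its time point, expected means and SDs, and a patient number. What is missing is its place among the analyses, its status and a rule for reading it.

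A reader might also infer that the plan intends to judge similarity from the two control p-values. No section says so. The cases in Step 3 are hypothetical and assume equal SDs, whereas the cited SDs are unequal. They show why the listed tests cannot substitute for the contrast, not an error that the plan commits to.

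Finally, because the clinician chooses the narcotic, a between-drug contrast is open to confounding. That is true, but the two listed control comparisons share the weakness. It calls for a label, not an omission.

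**Conclusion.** The point holds as an incomplete specification. The plan names and sizes a fentanyl-versus-morphine comparison but specifies no analysis of it and no rule for interpreting it, and the two listed tests cannot supply the answer. The formal hypothesis is not affected.

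This conclusion rests on the text alone. It does not depend on whether 74 is correct or on the ticagrelor figures. The 0.312 SD threshold assumes 80 evaluable patients per arm and equal SDs. The power figures also assume that the ticagrelor results transfer to aspirin and arachidonic-acid aggregation, which the documents do not establish.

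A reader might take the addition of the contrast to mean that similarity could then be declared. It could not: the documents give no margin, and a non-significant difference does not show similarity.

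This should be fixed, but it is not disabling: all three arms and the 2-hour outcome are already planned. Covariate adjustment, the timing of the 0-hour draw and the recording of draw times are separate questions and add no weight here.

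**What to change.** Amend the Data Analysis Procedure as follows.

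1. Add the fentanyl minus morphine difference in 2-hour arachidonic-acid aggregation, with its 95% CI, as a prespecified comparison. Label it non-randomised, since which "narcotic is administered will be up to the clinician".
2. Keep the two comparisons with no narcotic for the formal hypothesis.
3. State that any conclusion about similarity or difference between the drugs rests on the interval in item 1, not on the pattern of p-values against control. Make no equivalence claim unless a margin has been justified in advance.
4. State the status of the contrast and how alpha is handled across the three comparisons. This is needed even if no p-value is reported, because a 95% CI that excludes zero is a two-sided test at 0.05.

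**Cost.** The change is to wording only: the estimate uses data already planned and needs no extra patients. The downside is an estimate that is non-randomised and imprecise (half-width about 0.31 SD at 80 per arm). Its power, if the ticagrelor figures carry over, falls from about 80% to about 65% if alpha is split equally over three tests.
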